2.1.2 Clinical Experience

[¹¹C]MRB can be used to image NET-rich regions in the body at rest. Using a rodent model, [¹¹C]MRB PET imaging has been shown to appropriately 1) identify NET-rich regions in the body including BAT, heart, liver, pancreas, and kidney, 2) NET could be used as a highly specific target for BAT, and 3) that BAT can be detected in rodents under both room temperature and cold conditions ²⁴. Furthermore, the binding of [¹¹C]MRB in BAT was completely abolished by the pretreatment with a NET inhibitor, demonstrating the specific binding of the proposed ligand to BAT ²⁴. Building upon those rodent studies, the use of [¹¹C]MRB for imaging human BAT was validated under both cold and room temperature (RT) conditions at rest ¹². Ten healthy, Caucasian subjects (5M/5F: age 25±3, BMI 22±3 kg/m²)

HIC 2000030749

underwent [¹¹C]MRB PET-CT imaging for cervical/supraclavicular BAT under RT and cold-stimulated conditions (RPCM Cool vest; enthalpy 15°C) compared to ¹⁸F-FDG PET-CT imaging. Uptake of [¹¹C]MRB, was quantified as the distribution volume ratio (DVR). As seen in Figure 1, BAT [¹¹C]MRB binding was similar under both RT and cold conditions (BAT DVR: RT 1.0±0.3 vs. cold 1.1±0.3, $p=0.31$). Importantly, BAT DVR [¹¹C]MRB at RT correlated positively with body temperature ($r=0.92$, $p=0.004$).

Figure 1. A) Representative subject during scanning at RT and cold; B) [¹¹C]MRB Distribution Volume Ratio (DVR) in all subjects at RT and cold, closed marker = female

Obesity is associated with marked decrease in [¹¹C]MRB binding of human BAT. Recently, we have shown that there is a marked difference in [¹¹C]MRB binding of BAT amongst obese compared to lean women ² (Figure 2). In this proof of concept study, 15 healthy, non-diabetic Caucasian women (9 lean, age 25.6 ± 1.7, BMI 21.8 ± 1.3 kg/m² and 6 obese age 30.8 ± 8.8 BMI 37.9 ± 6.6 kg/m²) underwent PET-CT imaging of the neck/supraclavicular region using [¹¹C]MRB under RT conditions. We observed that [¹¹C]MRB binding was reduced in women with obesity in comparison to the lean group suggestive of decreased BAT. However, it remains to be determined whether NET in BAT is also reduced in men with obesity.

[figure not shown]
Figure 2. Decreased [¹¹C]MRB binding in BAT in women with obesity. A) Two representative subjects; B) All subjects.

Lean female participant

[figure not shown]

Fig. 3a

Muscle DVR v BMI

Obese female participant

Obesity is associated with altered [¹¹C]MRB binding

in skeletal muscle. Because SNS innervation of skeletal muscle has been shown to modulate skeletal muscle insulin resistance, we also performed preliminary analysis of ¹¹CMRB binding

HIC 2000030749

in muscle in these lean and obese women. In women, skeletal muscle (deltoid area) [¹¹C]MRB DVR correlated with BMI (Figure 3a), and was marginally lower ($P=0.088$) in women with obesity compared with women with normal BMI.

[figure not shown]
Based on these initial results, our goal is to expand our understanding of the importance of NET-binding in peripheral tissues (BAT and WAT) and skeletal muscle in obesity which may play a role in the pathogenesis of obesity-associated insulin resistance, type 2 diabetes and hypertension. We plan to perform whole body [¹¹C]MRB PET imaging to quantify NET-binding (an indicator of sympathetic activation of target organs) during rest in the fasted state in individuals with both normal BMI and with obesity. Furthermore, because in the past only women were included in our preliminary obesity study, we plan to determine whether [¹¹C]MRB binding in BAT will also be decreased in men with obesity ².

Furthermore, to validate NET as an indicator of SNS activity, we plan to correlate the results from the whole body [¹¹C]MRB PET

imaging scans with established measurements of SNS, such as heart rate variability, plasma catecholamine levels and MSNA ²⁹. [name], one of the co-investigators in this project, is an expert in human studies of the autonomic nervous system. Her laboratory has used microneurography to measure MSNA in women with obesity ³⁰. The bottom tracing in Figure

[figure not shown]
4 shows sympathetic bursts as measured by microneurography in the peroneal nerve of an obese human while resting. The other tracings show

beat to beat blood pressure, EKG and respiration. In our studies, we will examine changes in burst activity to determine changes in MSNA.

Human obesity is associated with altered brain NET. Central noradrenergic neuronal dysfunction has been observed in obesity ^{26,31-33}. Li et al ²⁶ demonstrated that obese subjects have decreased NET-availability in the thalamus (a sensory relay region in the brain); although these findings were not confirmed in a European cohort ³⁴. Vettermann et al ³⁵ showed that NET activity in the insula and hippocampus predicts successful weight loss. Furthermore, NET inhibitors used for the treatment of attention deficit disorder (ADHD) can promote weight loss ^{36,37}. In a prior study from our group ²⁵, we observed that NET in the hypothalamus correlated with counterregulatory hormonal and metabolic response to hypoglycemia (a stimulus to induce stress response

and increase hunger) ²⁵ (Figure 6). However, it is not clear whether NET- rich regions in the CNS,

HIC 2000030749

[figure not shown]
such as hypothalamus, thalamus, and brain stem (areas involved with glucose metabolism and autonomic function) are important in regulating SNS activation of target organs. We plan to investigate the relationship between CNS NET-availability and peripheral NET (measured by whole-body ($[^{11}\text{C}]$ MRB PET imaging) and SNS activity (measured by MSNA) both in normal BMI and obese individuals. We propose that CNS NET-availability at rest in the fasting state in the hypothalamus and thalamus (brain regions involved with glucose and energy metabolism) will correlate with NET binding in BAT and skeletal muscle in individuals with normal BMI. In contrast, because of obesity-associated regionalized SNS dysfunction, CNS-NET availability will not correlate with peripheral NET-binding or MSNA in individuals with obesity.

High carbohydrate meal ingestion is a strong stimulus for activation of the SNS. Food intake (in particular carbohydrate-rich meals) is a strong stimulus for activation of SNS in both animals³⁸ and humans³⁹⁻⁴². This has been demonstrated by plasma NE tracer kinetics^{38,39} and MSNA^{39,41-43}. In rodents, NE turnover in BAT, but not in the spleen or heart, increased in response to a meal³⁸. Regionalized SNS activation was also observed in humans: increased in skeletal muscle and kidneys, but no or minimal change in heart and liver³⁹. SNS play a major role in activating BAT after a meal⁴⁴, and a recent study using PET Imaging showed increased BAT activation after ingestion of a high carbohydrate-rich meal⁴⁵.

Food-stimulated SNS activation in obesity. Studies using MSNA have shown that obesity is associated with SNS hyperactivity in the fasting state^{17,18}. However, food-stimulated increments in MSNA have been shown to be blunted in individuals with obesity^{15,27}. Yeckel et al.²⁸ measured sympathetic activity

during exercise with the exercise recovery index – calculated by a ratio of heart rate normalized for oxygen consumption (VO₂). Sympathetic activity in response to exercise was compared with metabolic response in response to an OGTT and a high-carbohydrate meal challenge. The authors observed that insulin levels after the OGTT and test meal correlated with degree of sympathetic overactivity (Figure 9). Increased body fat (measured by densitometry) was associated with exercise-induced sympathetic overactivity. Therefore, based on the premise that obesity is associated with fasting SNS

Figure 9. Relationship between sympathetic activity (HR/V₂ O₂ plateau) and insulin levels OGTT and high-carbohydrate meal

hyperactivation and diminished increment in SNS activation in response to a food challenge (high-carbohydrate mixed meal test), we plan to measure $[^{11}\text{C}]$ MRB-binding in response to a meal in individuals with obesity in comparison to a group of individuals with normal BMI. In addition, to confirm the degree of SNS dysfunction in obesity, MSNA will be measured under similar circumstances (before and after a high-carbohydrate meal test).

HIC 2000030749

In our pilot study, sex differences were observed in response to a cold stimulus, with men showing a significantly increased [¹¹C]MRB-binding in response to cold ¹². Therefore, we will also investigate whether sex differences may play a role in [¹¹C]MRB-binding in response to a food stimulus. To build on our preliminary studies, we plan to quantify NET in peripheral tissues (adipose tissue (BAT and WAT) and skeletal muscle) and CNS at rest in fasting and post-prandial state, in both men and women with normal BMI and with obesity.

2.2 Background/prevalence of research topic

Obesity affects more than a third of the population of the United States ⁴⁶ and carries an increased risk of developing type 2 diabetes, hypertension, heart disease, stroke, and certain types of cancers ⁴⁷. However, the exact mechanisms by which obesity contributes to these cardiometabolic disorders remains uncertain. Sympathetic nervous system (SNS) dysfunction has been described in individuals with obesity ¹⁵⁻¹⁸ and it has been proposed as one of the mechanisms involved in the development of obesity-related cardiometabolic complications ^{20,21}. It was initially proposed that obesity was associated with decreased SNS activity with a consequent decrease in energy expenditure and weight gain ⁴⁸. However, these findings were not confirmed by other reports. Some studies showed no change or even increased SNS activity (measured by plasma norepinephrine levels) ⁴⁹. Studies using microneurography, a direct measurement of SNS activation, showed that individuals with obesity may have sympathetic overactivity ^{17,18}. SNS activity may vary by tissue ^{21,50}. Specifically: SNS activation increases in kidneys and skeletal muscle and decreases or is unchanged in heart, and mostly unchanged in adrenal glands. Regionalized SNS hyperactivity in kidneys and skeletal muscle may lead to hemodynamic and metabolic changes in individuals with obesity. This results in an increased risk of developing hypertension and diabetes, and, in turn, cardiovascular morbidity and mortality. However, it is not exactly clear the interplay between obesity and regionalized SNS dysfunction. We propose that obesity is associated with dysfunctional coordination of SNS activation; and to prove that, we plan to measure synchronous SNS activity in various target organs in healthy individuals with normal body mass index (BMI) and with obesity.

SNS activation of target organs is mediated principally by the neurotransmitter norepinephrine (NE). Noradrenergic neurons release NE in the neuronal synapse of target organs and NE reuptake by pre-synaptic norepinephrine transporters (NET) are important for regulating NE levels in the synapse and neurotransmission ²². NET availability is thus considered a marker of neuronal activation ²². Our group has validated the use of [¹¹C]MRB which has high specificity for NET. In a rodent model, this tracer properly identified NET-rich regions in the body, such as brown adipose tissue (BAT), white adipose tissue (WAT), skeletal muscle, liver, heart, and brain ²⁴. In humans, [¹¹C]MRB has been used to quantify unstimulated BAT in men and women ⁵¹, and NET availability in BAT from healthy women with obesity was found to be reduced in comparison to healthy women with normal body mass index (BMI) ². In addition, preliminary unpublished data from our group showed that, in women, NET

HIC 2000030749

availability in skeletal muscle (deltoid) inversely correlated with BMI. [¹¹C]MRB PET imaging allow us to properly identify NET-rich regions in both in humans and animals and may be used as a novel technique to quantify SNS activation of target organs. Furthermore, we will investigate whether NET activity (as measured by [¹¹C]MRB PET imaging) correlates with muscle sympathetic nerve activity (MSNA), the gold-standard measurement for systemic SNS activation. Altered coordinated SNS multi-organ activation in the fasting and post-prandial state in obesity may play a role in the pathophysiology of obesity-associated cardiometabolic disorders.

There is also compelling evidence that SNS activity is not only altered at baseline in obesity but also in response to stimuli. Studies have found that obesity is associated with altered SNS responses to various stimuli including oral glucose, food, hyperinsulinemic-euglycemic clamp ^{15,27,28,52}. Food-stimulated increments in MSNA have also been shown to be blunted in individuals with obesity ^{15,27}. Thus, we plan to simultaneously measure NET-binding in BAT, WAT, skeletal muscle, and brain in the fasted state and after a high carbohydrate meal challenge. Furthermore, we will evaluate the relationship between NET-rich regions in the brain involved in energy homeostasis (such as hypothalamus) and motor and sensory relay (thalamus) with peripheral NET-rich tissues, such as BAT and skeletal muscle

3 Rationale/Significance

3.1 Problem Statement

Sympathetic nervous system (SNS) dysfunction has been observed in obesity and may play a role in the pathophysiology of obesity-associated cardiometabolic disorders.

3.2 Purpose of Study/Potential Impact

This project will help further understand the impact of obesity in SNS activity and better understand the role of the SNS in the development of cardiometabolic disorders in patients with obesity.

3.2.1 Potential Risks

Risks Associated with Radiation:

Yale University Radioactive Investigational Drug Committee (Yale RIDC) will review the use of radiation in this research study, and no subjects will be scanned until RIDC approval is obtained. This research study involves exposure to radiation from [¹¹C]MRB PET scanning. This radiation exposure is not necessary for medical care and is for research purposes only.

For each individual PET scan, subjects will receive up to \leq 20 mCi of, [¹¹C]MRB, plus transmission scans. This is equal to an effective dose of 0.428 rem per injection.

HIC 2000030749

Although each organ will receive a different dose, the maximum amount of radiation exposure subjects will receive from participating in up to two PET scans is equal to an effective dose 0.856 rem, for a total of up to 40 mCi of [¹¹C]MRB in 2 injections. This calculated value is used to relate the dose received by each organ to a single value.

Subjects will also receive radiation exposure from low dose whole-body CT scans on the mCT, subjects will receive up to 1250 mrem (1.250 rem) from up to 2 low dose head CT scans (0.625 rem each).

The maximum amount of radiation an individual subject could receive in this study is from up to 2 injections of \leq 20 mCi of [¹¹C]MRB, plus CT scans. This is equal to an ED of 2.106 rem.

The amount of radiation subjects will receive in this study is below the dose guidelines established by the RIDC guidelines for research subjects. This guideline sets an effective dose limit of 5 rem per year.

Adverse effects of the radiopharmaceuticals in this study have not been reported. However, the possibility exists for a rare reaction to any of the substances or procedures to which a subject is exposed.

Physical examination, venipuncture/IV placement, EKG, lab data collection and analysis: Subjects will receive a comprehensive medical history assessment, physical examination, EKG, and lab testing to ensure good physical health status and eligibility. These are routine medical procedures and should add no risks other than those normally associated with these procedures. Study doctors and/or nurse practitioners will assess the EKG and screening laboratory blood work. If any abnormal findings occur, they will provide appropriate medical advice. Potential participants who are excluded from the study due to medical reasons, or those who are in immediate need for medical or psychiatric attention, will be referred to the appropriate facilities at Yale New Haven Hospital so they can receive the clinical care needed to address their condition. Subjects will be exposed to the risk of venipuncture/IV placement that is routinely done in the HRU at the YNHH. Risks associated include: local bruising, hematoma, or infection. If this occurs, appropriate treatment will be provided immediately. On extremely rare occasions, a blood clot or infection might occur, and if this occurs, subjects will be treated at the HRU, which is fully staffed with nursing specialists and medical personnel. These risks are mitigated by the use of research HRU nurses who have extensive experience in venipuncture and IV catheterization. Transient vasovagal symptoms, e.g., nausea, sweating, and lightheadedness may also occur during IV catheter placement. Careful efforts to maintain confidentiality have been effective in previous research, and only patients' code numbers will be recorded on forms to protect confidentiality. Efforts to protect confidentiality are further detailed below.

Oral glucose tolerance test (OGTT): The OGTT is a commonly used outpatient test for diagnosis of type 2 diabetes. It is not associated with any specific adverse effects. Occasionally, some patients may experience mild nausea or GI discomfort following drinking the 75 gram glucose drink; however, this typically resolves after eating food.

HIC 2000030749

Microneurography: The risk of microneurography is a peroneal paresthesia for 2-10 days following the experiment. The incidence of paresthesia is reported to be less than 10%, in less than 1% of all subjects paresthesia can persist for up to two months. Paresthesia resolves spontaneously. Microneurography can occasionally be painful, but this is very unusual.

Phlebotomy: The total amount of blood drawn is ~160 ml (including screening, OGTT). People who are in good health are not usually affected by this kind of blood loss. However, to be safe, subjects will be warned against donating blood for at least 6 weeks before and after completing this study. Additionally, subjects are screened for anemia at the first visit and females with a hematocrit less than 35% and males with hematocrit less than 40% will be excluded.

DXA scanning: DXA scanning for body composition is performed routinely by our group. The DEXA measurement poses no major risk to the subject. The amount of radiation the subject will be exposed to is small and is one tenth of the amount of radiation for a chest X-ray.

Medical treatment for injury: The consent form will specify that medical therapy will be provided for injuries sustained as a consequence of participation in this research. This will be provided at the HRU located at the YNHH or Church Street Research Unit (CSRU).

Minimizing Risks:

General: All investigators and research team members have taken the Human Investigations Training Course either on-line or in person at the Yale School of Medicine. Trained medical staff at the HRU will perform all clinical research procedures and all subjects will have health screens reviewed by a physician or nurse practitioner prior to their participation. In the event of an injury, medical therapy will be offered with the cost incurred by the subject's medical insurance carrier. Confidentiality of all study information is maintained by identifying subjects by code numbers, which are subsequently linked to their data files. No individuals, other than professionals directly involved in the study will be allowed to read data forms to ensure confidentiality. No subjects are identified by name in published data and only by code in data storage areas.

Informed consent: All subjects are consented by one of the study investigators or research staff, as part of determining their study eligibility. The purpose, nature, and potential risks and benefits of the study will be explained to each potential subject in detail during the screening interview. Prior to initiating the study, one of the study investigators or research staff will explain the planned study interventions, and each subject will be asked to read and sign a consent form approved by the Yale School of Medicine Human Investigation Committee (HIC). All potential subjects are given ample time to ask questions and only after this are they asked to provide informed consent in the research study. Subjects are given a copy of the signed consent for their personal records.

IV Insertion and Blood Drawing: Risks of bruising, clotting, and infection will be minimized by having venipuncture performed by trained, experienced personnel under sterile conditions. To avoid injury due to fainting, the antecubital vein catheter will be inserted when the subjects are recumbent. Females with a hematocrit less than 35% and males with a hematocrit less than 40% will be excluded. All subjects having donated blood within 6 weeks of the study will be

HIC 2000030749

asked to postpone study participation (with a repeat blood count prior to future enrollment), and patients will be advised to refrain from blood donation for 6 weeks after each study.

Radiation. The Yale-New Haven Hospital Radiation Safety Committee (RSC) will review the use of radiation in this research study, and no subjects will be enrolled until RSC approval is obtained. This research study involves exposure to radiation from DXA scan and [¹¹C]MRB PET scanning. This radiation exposure is not necessary for medical care and is for research purposes only. The targeted amount of radiation an individual subject will receive in this study is from 2 injection(s) of \leq 20 mCi of [¹¹C]MRB plus transmission scans and CT scans CT scans for attenuation correction and DXA scan. All scans will be done in the presence of medical supervision and trained nursing staff in an institution specifically designed to support imaging studies. In the event of serious medical complications, the Yale University PET scan facilities have immediate access to or consultation with specialized medical units at the Yale-New Haven Hospital. Preparation of radiopharmaceuticals and performance of PET scans will be by radiochemists and technologists of the Department of Diagnostic Radiology, Yale University School of Medicine. These professionals are qualified by training and experience in the safe use and handling of radiopharmaceuticals. Subjects will be asked about their previous radiation exposure, and those who have had research exposure within the past year will be excluded if their cumulative annual exposure (including the present study) exceeds FDA limits. No PET studies will be performed on pregnant or potentially pregnant women, as confirmed by pregnancy testing during evaluation and on each scan day before initiation of any scan procedures. If subjects are breastfeeding they will not be able to participate in this research study.

Microneurography. The likelihood of the occurrence of symptoms following microneurography will be minimized by the following certain procedures. First, few problems or symptoms are reported in laboratories whose microneurographers have received training from individuals with a documented record of success and safety. [name] or [name] will perform all microneurography studies. [name] is a highly qualified microneurographer in the laboratory with over two years' experience, and [name] has performed microneurography in her laboratory for 10 years, and this will reduce the risk of occurrence of symptoms following the experiment. The time spent searching for a nerve fascicle within the peroneal nerve will be limited to $<$ 60 min. No nerve site will be sampled more than once. The recording electrodes are inspected under a dissecting microscope to ensure electrode tip integrity (those electrodes found with damaged tips are not used) and each recording electrode will be used only once for intraneuronal recording. Placement of the electrodes and positioning in the common peroneal nerve are performed under sterile conditions. Metal microelectrodes are steam sterilized at Yale New Haven Hospital before use. The site of electrode placement is cleaned with alcohol and only investigators wearing sterile gloves handle the sterile microelectrodes. Following these simple guidelines, the risk of occurrence of symptoms following microneurography will be small. Microneurography studies are conducted at the Pierce Laboratory.

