High Carbohydrate Mixed meal test (MMT): Two weeks after visit 2, participants will come to the PET Center after a 10-hour overnight fast. A nurse will insert an intravenous (IV) catheter and subjects will ingest a liquid meal (65% CHO, 20% fat, and 15% protein, equal to 40% of daily energy expenditure, per ~16 ounces) to be prepared by the Metabolic Kitchen located at the HRU. Blood samples will be collected at -10, 0, 15, 30, 60, 90, and 120 min for measurement of glucose, insulin and C-peptide concentrations ⁷. Plasma samples will be drawn at baseline and throughout the MMT for measurement of additional hormones (such as leptin, ghrelin, thyroid hormones, and catecholamines) and free fatty acids (FFA) levels. Insulin and glucose will be used to calculate indexes of insulin sensitivity ⁷⁻⁹. Hormones, glucose and FFA will be correlated with PET measurements of brown fat at baseline and during the MMT. Approximately 60 mL of blood will be drawn at this visit.

HIC 2000030749

Participants will undergo whole body [¹¹C]MRB PET scan as described in visit 3. After the MMT, PET data will be acquired dynamically for 120 min using the Siemens mCT-X whole-body PET/CT scanner after an intravenous bolus dose of MRB (~20mCi).

The order of the PET scan visits 2 and 3 will be randomized.

PET and MSNA visits do not need to occur in sequence, i.e. PET scans can occur before or after the MSNA.

Measurement of Energy Intake: Hunger and fullness will be determined immediately before, during and after the PET scans with Visual Analog Scales (VAS).

Visit 4 – Sympathetic Nervous System Activity (SNSA) measurement Visit - Fasting

Two weeks after visit 3, participants will be asked to return for a separated visit for measurements of SNS activity at rest and fasting. This visit will be performed at the Pierce Laboratory ([name] laboratory). The participants will come in the morning (~9am) and will be asked to fast for 10-hour and to maintain their regular exercise routine. The following measurements will be obtained: MSNA, heart rate (HR), blood pressure (BP), electrocardiogram (EKG), and heart rate variability. The proposed procedures will be performed at fasting (baseline). Participants will be asked to maintain their regular exercise routine.

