6.3.5 On Study Visits

Screening

- Consent
- Urine Pregnancy test for women of child-bearing potential
- Height and Weight using Tanita Scale
- EKG
- IV Insertion and OGTT
- Blood draw for anemia, kidney and liver function and thyroid test and diabetes
- Physical & Medical History
- DXA Scan

Visit 2 & 3 PET Scans

- Subject will arrive to PET Center, fasted
- Urine Pregnancy Test for women of child bearing potential
- Urine Drug Screen
- A-line and IV insertion
- Mixed Meal Test on Visit 3
- A low dose CT scan will be completed immediately before or after each PET scan.
- Up to 3-4 hour PET scan
- Collection of Blood Sampled during PET scan
- Light Lunch given to subject after PET Scan

Visits 4 & 5

HIC 2000030749

- Subject will arrive fasted to the Pierce Laboratory for measurements SNS activity
- Urine Sample Collection
- Collection of Weight
- Collection of the following: Microneurography, BP, HR
- EKG
- IV Insertion
- Blood Sample
- Measurement of skin blood flow
- Sympathetic Nervous System Activity (SNSA) measurement

Visit 1: Screening Visit
 
 -Review of Consent Form -Physical and Medical history review -Pregnancy Test (females) -EKG -Blood Work -OGTT -Body Composition 
 -Tanita Scale -DXA Scan 	
Visit 2: Whole body PET/CT
 
Imaging
 
Fasting Visit
 
 - Urine Pregnancy Test (females) - Urine Drug Screen - [¹¹C]MRB - Low dose CT scan and PET scan - Norepinephrine levels (serum) 	
Visit 4: SNSA Visit – Fasting
 
 - BP, HR, PI, HR variability - EKG - MSNA
	
Visit 3: Whole body PET/CT
 
Imaging
 
Mixed Meal Test Visit
 
 - [¹¹C]MRB - Urine Pregnancy Test (females) - Urine Drug Screen - Ingestion of mixed meal - Measurement of Energy Intake - Low dose CT scan and PET scan - Norepinephrine levels (serum) 	
Visit 5: SNSA Visit - Mixed Meal Test
 
 - Ingestion of mixed meal - BP, HR, PI, HR variability - EKG - MSNA

Abbreviations: BP=blood pressure, EKG=electrocardiogram, HR=heart rate, MSNA=Muscle sympathetic nerve activity, SNSA=Sympathetic Nervous System Activity

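### Section 6.3.5 lists an undefined A-line (ordinarily an arterial line) at both PET visits with no stated use or arterial risk text, and the ~160 mL blood total in 3.2.1 omits Visit 2

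*Combined protocol and SAP*

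**What the plan says.** Section 6.3.5 On Study Visits has one list for Visits 2 and 3 together. It includes "A-line and IV insertion", "Collection of Blood Sampled during PET scan" and "Up to 3-4 hour PET scan". The one item that belongs to a single visit is marked as such: "Mixed Meal Test on Visit 3".

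The detailed visit descriptions (Synopsis, 5.1 and 6.3) do not mention an arterial line. For the meal PET visit they say "A nurse will insert an intravenous (IV) catheter"; for the fasting PET visit they describe only an intravenous tracer injection. PET quantification is by MRTM2 with the occipital cortex as reference region.

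In 3.2.1 Potential Risks, the text on lines is venous. The risk paragraph says "Subjects will be exposed to the risk of venipuncture/IV placement that is routinely done in the HRU at the YNHH", and the precautions say that "the antecubital vein catheter will be inserted when the subjects are recumbent". The Phlebotomy paragraph gives the study total: "The total amount of blood drawn is ~160 ml (including screening, OGTT" and so on.

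The visit text states approximate blood volumes for Visits 1, 3, 4 and 5 and none for Visit 2. The schedule figures (Synopsis, 6.2, 6.3.1 and 6.3.5) nevertheless list a norepinephrine level at Visit 2.

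**The concern.** Two items in the PET-day checklist have no counterpart in the risk section.

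The first is the A-line. It is listed beside the IV, so it is something other than the IV, and it carries no restriction to one visit. Arterial cannulation is more invasive than venous access. The participants are healthy volunteers, and 3.2.2 says that they gain no direct benefit. A team working from the 6.3.5 checklist could place a line that the rest of the protocol neither describes nor uses, and anyone weighing risk from 3.2.1 would not know that it was planned.

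The second is the blood total. It is the figure on which the protocol's statement about tolerable blood loss rests, and it appears to leave out a visit at which blood is taken.

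**Working it through.** **Blood total**

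Inputs, each stated as approximate in 5.1 (and repeated in the Synopsis and 6.3):

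| Visit | Volume (mL) |
|---|---|
| 1, screening and OGTT | 40 |
| 2, fasting PET | not stated |
| 3, PET with meal | 60 |
| 4, SNSA fasting | 20 |
| 5, SNSA with meal | 40 |

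Reproducing the plan's figure: 40 + 60 + 20 + 40 = 160 mL, which matches 3.2.1 exactly. The implied allowance for Visit 2 is 160 − 160 = 0 mL. Yet the schedule lists norepinephrine at Visit 2, and 6.3.5 lists blood sampling during the scan at both PET visits.

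The corrected total is 160 mL plus the Visit 2 volume. The documents do not give that volume, so these values are assumptions:

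- 5 mL: 165 mL, and 5/160 = 3.1% above the stated total
- 10 mL: 170 mL, 10/160 = 6.25% above
- 20 mL (the volume at the fasting SNSA visit): 180 mL, 20/160 = 12.5% above

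Any arterial sampling would come on top. The documents also do not say whether the 60 mL at Visit 3 covers the in-scan sampling listed in 6.3.5.

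**A-line**

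1. *How many.* Section 5.3.1 plans 20 + 20 = 40 participants. There are two PET visits each, so a literal reading gives 40 × 2 = 80 cannulations, counting one per scheduled visit. If the item is not intended, the number is 0.
2. *Is it needed for the PET outcome?* DVR is V_T/V_ND, estimated by MRTM2 from the target region and the occipital reference region, with k2' fixed at 0.021 per minute. The K1 and V_T expressions in 5.1 serve to define the relative delivery R1 = K1/K1'. No plasma input is measured or modelled, and 6.4 and 6.5 specify no analysis with an arterial input function.
3. *Is it needed for the other blood samples?* The hormone and glucose sampling at Visit 3 follows insertion of an intravenous catheter. No sample is linked to an arterial line.
4. *Is the risk described?* 3.2.1 covers venipuncture, IV placement and an antecubital vein catheter. It has no arterial-specific risk or precaution. The other arterial references in the protocol are to blood pressure by finger cuff or sphygmomanometer at the SNSA visits, which are non-invasive.

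**The case against.** The strongest reply is that the A-line rests on one undefined abbreviation in a summary checklist, while the longer visit text, given three times, never mentions it. It may be a remnant of another protocol. The scan-duration item in the same list, against the 120 minutes of acquisition stated elsewhere, points that way, though weakly, because three to four hours could include set-up and the meal. This stands: the documents do not show that arterial lines are planned. It does not remove the point, because a checklist item for an invasive procedure has to be either deleted or explained.

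General safeguards also exist. Section 5.3.2 excludes bleeding disorders and anticoagulant use, and 3.2.1 places scans under medical supervision with trained nurses. Neither amounts to an account of arterial risk.

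On the blood total, the sum itself is correct, every volume is approximate, and the Visit 2 schedule names only norepinephrine. An extra 5 mL could be absorbed by the rounding, and no limit or stopping rule depends on 160 mL. This too stands: it is an omission of unknown and possibly trivial size, not an addition error.

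Two stronger readings are tempting and are not supported:

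- *A reader might infer that an ordinary line-site complication would have to be classed as unexpected.* The expectedness rule in 6.2.3 compares events with the risk information for the study intervention, in text concerned with the investigational product. The IRB-reporting criteria there also refer to the consent document, which is not available here. 3.2.1 already lists bruising, hematoma, infection and clot, although for venous access. Only arterial-specific harms lack a description.
- *A reader might infer that blood taken through the line would go unused.* Catecholamine and hormone assays are planned at the PET visits, and plasma hormones are secondary endpoints, so blood from any line could serve them. What is missing is a stated reason for an arterial line.

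**Conclusion.** The point holds in a limited form. Section 6.3.5 lists an A-line at both PET visits that has no stated purpose, no counterpart in the detailed procedures, no role in the planned quantification and no arterial-specific risk text. Its size is between 0 and 80 cannulations, depending on whether the item is a remnant or an intention; the documents do not settle which. This rests on reading A-line as arterial line, which is the ordinary meaning and is supported by its listing beside the IV.

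The ~160 mL total covers four of the five visits and omits a draw that the protocol schedules. The shortfall cannot be computed from the documents. With 5 to 20 mL assumed, the total would be 165 to 180 mL.

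Both are matters of participant safety and internal consistency. Neither affects power or the planned analyses, and nothing is claimed about the consent form.

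**What to change.** Delete the A-line from the PET-visit list in 6.3.5, since no planned analysis uses it. Only if arterial sampling is truly intended should it stay. In that case, describe it in 5.1 and 6.3 (site, number of samples, volume), state the analysis that uses it, and add arterial-cannulation risks and precautions to 3.2.1.

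In either case, state a Visit 2 blood volume in the visit text and raise the total in the Phlebotomy paragraph accordingly. State also whether the Visit 3 volume includes the in-scan sampling.

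The deletion and the corrected total cost a minor text amendment and a slightly higher stated blood volume. It is not entirely free, because 7.2 requires an approved IRB amendment for any protocol change. Keeping the A-line would cost more: a new risk paragraph, an added analysis and a larger blood total, and it might make recruitment harder.
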